5.8 Long-term Safety Outcomes (through 1 year)

- 1. Stroke
- 2. Transient ischemic attack (TIA)
- 3. Major vascular complications (MVC)
- 4. Renal complications

PATIENT POPULATION AND SELECTION 6

6.1 Patient Population

Adult patients age \geq 18 years at time of screening with primarily functional MR (\geq 3+) and symptomatic heart failure despite guideline directed medical therapy (GDMT) should be considered for inclusion in this trial. Patient will be considered enrolled in the study at the time written informed consent form (ICF) is signed and will be assigned a patient ID in the electronic data capture (EDC) system. Patients that sign the ICF, but are found ineligible during the screening process, will be considered screen failures. Screen failures will not be counted towards enrolled roll-in patients or the pre-planned sample size (i.e., the enrollment will continue until the pre-planned 375 non-screen failures are enrolled). If a patient is identified as a screen failure during the index procedure (prior to placement of the system into the body), the patient shall be followed for 30 days for the purposes of safety evaluations only and will be reported upon as a separate Screen Failure cohort safety analysis.

In studied populations the average age of patients with mitral regurgitation is 67 (± 12.7) years⁴. This study is expected to enroll patients with baseline characteristics (e.g. age) similar to previously studied populations, and results are expected to be generalizable to individuals qualifying for Medicare based on age criteria.

6.2 Inclusion Criteria

Patients must meet all of the following criteria to be eligible for the study:

Inclusion	Criteria	Window/Guidance
Criteria #		
1.	Eighteen (18) years of age or older;	As of date of signature on informed consent
2.	Clinically significant functional MR (≥ 3+ by echocardiography) as assessed by the core lab;	
3.	Stable heart failure medications as determined by local heart team;	Stable for 30 days prior to procedure date (further details in Section 8.3)
4.	Elevated BNP > 150 pg/ml or corrected NT-proBNP > 600 pg/ml within past 90 days or heart failure hospitalization within past 12 months;	Elevated BNP or NT-proBNP measured no earlier than 90 days prior to date of informed consent OR heart failure hospitalization within past 12 months prior to informed consent.
5.	Symptomatic heart failure patients with measured baseline 6 minute walk test (6MWT) between 150 and 400 meters;	
6.	Patient is deemed appropriate for Edwards Cardioband System by the Heart Team at the investigational site and the Central Screening Committee;	
7.	Patient is able and willing to give informed consent and follow protocol procedures, and comply with follow-up visit compliance.	

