6.7 Technical Feasibility Assessment of Edwards Cardioband System Implantation by **Sponsor**

The Sponsor will review applicable patient data collected at Screening and Baseline Visits (e.g. cardiac CT) to determine the technical feasibility of implanting the Edwards Cardioband System. The Sponsor may also assist the site in determining the most appropriate implant size for the patient.

Central Screening Committee Determination

After the Central Screening Committee (CSC) has reviewed all screening and baseline assessments and reached a decision on eligibility, the decision will be communicated to the site. The site will proceed to scheduling the case for approved patients in accordance with institutional procedures.

^{*}If TTE is more than 60 days from the procedure, a repeat TTE will be required.

Randomization Procedure 7

Patients will be prospectively randomized into the clinical study. Randomization will occur only after the patient provides informed consent, completes all required screening and baseline procedures, and satisfies the study eligibility criteria (including eligibility determination by the Central Screening Committee). Randomization shall be performed after cases have received final approval from the CSC and Sponsor and the case has been scheduled at the institution.

Eligible patients will be randomly assigned in a two to one (2:1) ratio to either treatment with Edwards Cardioband System + Guideline Directed Medical Therapy (Device Group) versus Guideline Directed Medical Therapy alone (Control Group).

Randomization assignment will be generated via the randomization module of the EDC system. Randomization scheme will be based on random blocks and will be stratified by:

- study center
- baseline ischemic vs. non-ischemic disease

This randomization schedule (list) will be masked to study patients, site personnel, study team and Sponsor. Only the un-blinded statistician and designates will be privy to the masked randomization scheme.

A patient is not considered randomized until the randomization assignment has been dispensed. If at any time after randomization a patient becomes ineligible or withdraws, the patient is still considered randomized.

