Survival analysis techniques will be used to analyze the time-to-event variables. Patients without events will be censored at their last known event-free time point. If this event-free time point occurs after the analysis time point, the days to event variable will be set equal to the analysis time point so that the patient will be included in the analysis. For patients who did not have an event or early withdrawal and have not yet completed the analysis visit, they will be censored at the time of their last follow-up. Time to first event curves will be constructed using Kaplan-Meier estimates and all post discharge results will be summarized with Kaplan-Meier estimates of event rates. Hazard ratios, confidence interval for the hazard ratios, and p-values may also be presented from a Cox proportional hazards model.

Covariate analyses and variables of interest, as well as possible subgroup analyses of interest, may be performed to gain more clinical insight.

Descriptive statistics will be presented at each assessment, including change from baseline to subsequent time point for selected endpoints. Paired (i.e., patients with available data at both baseline and respective time point) and unpaired data will be presented separately.

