### 8.4 Key Secondary Efficacy Endpoints (1 Year)

Secondary efficacy endpoints will be tested in hierarchical order after the primary endpoints to address multiplicity and preserve alpha at the .05 level. When one of the endpoints does not achieve statistical significance in favor of the Device group, no further testing of subsequent endpoints will be conducted.

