### f. Heart Failure Hospitalizations

The number of heart failure hospitalizations between day 0 and day 365 post procedure will be quantified as recurrent events and analyzed with a survival analysis intensity model (Andersen and Gill, 1982). The null ( $H_0$ ) and alternative ( $H_1$ ) hypotheses are:

H0: HR = 1 H1: HR ≠ 1

HR represents hazard rate for Device group relative to Control group. A two-sided alpha of 0.05 will be used.

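### The gated HF-hospitalization test names no baseline covariate and no robust variance; adjusting for prior-year HF hospitalization would sharpen it modestly, but only if a robust variance is specified too.

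*Protocol*

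**What the plan says.** - **Entry.** Protocol 6.2, inclusion 4, requires "Elevated BNP > 150 pg/ml or corrected NT-proBNP > 600 pg/ml within past 90 days or heart failure hospitalization within past 12 months". The guidance column times the second route as "heart failure hospitalization within past 12 months prior to informed consent". The routes are joined by "or", so a patient may qualify by either or both.
- **Randomization.** Protocol 7 and SAP 2.3 stratify by center and "baseline ischemic vs. non-ischemic disease". Prior HF hospitalization is not a stratum.
- **Test.** Under SAP 8.4f the one-year HF hospitalizations are "quantified as recurrent events and analyzed with a survival analysis intensity model", and "A two-sided alpha of 0.05 will be used". Neither SAP 8.4f nor Protocol 13.4.4 names a covariate, a stratum or a variance estimator.
- **Gate.** The test is sixth of eight in a fixed sequence that follows both co-primary endpoints. After a failure, "no further testing of subsequent endpoints will be conducted" (SAP 8.4).
- **Covariates.** Protocol 13.4.1 leaves covariates to be pre-specified in the SAP. SAP 6.1 says only that such analyses "may be performed to gain more clinical insight" and lists none. SAP 10 reports a single difference from the protocol, which concerns roll-in patients.

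**The concern.** Prior-year HF hospitalization is the baseline counterpart of the outcome being tested. If it predicts later events, a model without it leaves a known source of between-patient variation in the error, so the test is weaker and the interval wider than they need be. The protocol reserved a place for such a covariate and the SAP left it empty, so any later choice would be made with the data in hand. The planned counts are also strongly overdispersed. This makes the unstated variance estimator matter more than the covariate, because it decides whether the test keeps its level and whether adjustment shows up in the standard error at all.

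**Working it through.** **The plan's own figure.** No power is stated for this test, although Protocol 5.4 and SAP 3.6 head these endpoints as powered. The only stated power that uses the HF counts is for co-primary II at 300 evaluable patients: above 90% in the synopsis, 87% in Protocol 13.5 and SAP 8.11. Simulating the Finkelstein-Schoenfeld test on the listed assumptions (5,000 trials, components independent, uniform death times) gave 94%. That reproduces the synopsis figure but not the 87%, which is a separate matter.

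**Inputs (SAP 8.11).** Patients with 0/1/2/3/4/5+ HF hospitalizations: Control 60/10/10/10/5/5%, Device 70/10/5/5/5/5%. Allocation is 2:1, with 375 enrolled and 300 evaluable. I take 5+ as 5 and assume complete one-year follow-up.

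**Moments.**
- Control: mean 0.10 + 0.20 + 0.30 + 0.20 + 0.25 = 1.05; variance 3.45 − 1.05² = 2.3475.
- Device: mean 0.10 + 0.10 + 0.15 + 0.20 + 0.25 = 0.80; variance 2.80 − 0.80² = 2.16.
- Rate ratio 0.80/1.05 = 0.762, log −0.272. Variance/mean is 2.24 (Control) and 2.70 (Device); a Poisson count would give 1.

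**Unadjusted test, robust variance.** Var(log rate ratio) = 2.16/(n_D × 0.80²) + 2.3475/(n_C × 1.05²).
- 250:125: 0.0135 + 0.0170 = 0.0305, SE 0.175. Power = Φ(0.272/0.175 − 1.96) = 34%.
- 200:100: 0.0169 + 0.0213 = 0.0382, SE 0.195. Power = 28.5%.

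**Unadjusted test, model-based variance.** At 250:125, SE = √(1/(250 × 0.80) + 1/(125 × 1.05)) = √(0.0050 + 0.0076) = 0.112, about two-thirds of the robust value. If both arms follow the Control counts, the type I error is 2 × [1 − Φ(1.96/√2.24)] = 19%, not 5%.

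**Effect of the covariate.** Let p be the prevalence of a prior-year HF hospitalization and r the rate in those patients relative to the others. Both are assumptions. The squared between-group coefficient of variation is B = p(1 − p)(r − 1)²/[1 + p(r − 1)]². Adjustment removes B × (1/250 + 1/125) = 0.012 B from the robust variance at 375. The proportional cut is the same at 300.

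| p | r | B | Variance cut | Power at 375 | Power at 300 |
|---|---|---|---|---|---|
| – | 1 | 0 | 0% | 34.3% | 28.5% |
| 0.3 | 1.5 | 0.040 | 1.6% | 34.8% | 28.9% |
| 0.5 | 1.5 | 0.040 | 1.6% | 34.8% | 28.9% |
| 0.3 | 2 | 0.124 | 4.9% | 35.8% | 29.7% |
| 0.5 | 2 | 0.111 | 4.4% | 35.6% | 29.6% |
| 0.5 | 3 | 0.250 | 9.8% | 37.4% | 31.1% |
| 0.3 | 3 | 0.328 | 12.9% | 38.5% | 32.0% |

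Over r = 2 to 3 the cut equals about 375 × (1/0.956 − 1) = 17 to 375 × (1/0.871 − 1) = 55 extra patients. Simulations that keep the plan's count distribution agree: relative efficiency was about 1.00-1.01 at r = 1.5 and 1.03-1.15 at r = 2 to 3, for prevalence 30-70%.

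**Which standard error shrinks.** In simulations at 250:125 (Poisson analogue, complete follow-up) the model-based SE was about 0.113 with and without the covariate. Only the robust SE fell, from about 0.176 to 0.165-0.175.

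**The case against.** The strongest reply is that an unadjusted comparison of randomized arms is valid, that the plan uses unadjusted tests for every key secondary endpoint, and that one covariate for one endpoint is an efficiency preference. That stands as far as it goes: omitting the covariate is a missed gain, not an error. What tips the balance is the open commitment in Protocol 13.4.1 and the near-zero cost.

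Four stronger readings are tempting, and the documents do not support them.
- *The entry item divides the cohort by risk.* No section gives its prevalence or links it to later HF hospitalization. Every patient without a prior hospitalization must have a raised natriuretic peptide, itself a selection that may narrow the contrast. At r = 1.5 the gain is negligible.
- *Adding the covariate by itself narrows the interval.* It does so only under a robust variance; the model-based SE stays where it was.
- *The lost precision blocks the mortality endpoints behind the gate.* The plan assumes equal all-cause (20%) and cardiovascular (15%) mortality in the two arms, so no planned mortality effect lies there.
- *The test will run at a 19% type I error.* The SAP is silent on the variance, so this is what a model-based analysis would do, not what the plan says will be done.

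**Conclusion.** The point holds as a modest improvement worth making. The gated test pre-specifies no covariate, the obvious candidate is an entry item, and the SAP does not deliver what the protocol left to it. The gain is about 0-4 power points from a base of 29-34%, conditional on 30-50% prevalence and a rate ratio of up to 3. It also rests on the plan's counts with 5+ taken as 5, and on complete follow-up despite the planned 20% mortality. Adjustment does not rescue the test: 80% power on the planned counts would need about 1,218 patients unadjusted. The robust variance is the essential part of the change. Without it the level of the test is not protected and the covariate's benefit does not appear.

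**What to change.** In SAP 8.4f and Protocol 13.4.4, fit the Andersen-Gill model with HF hospitalization in the 12 months before consent (yes/no) as a pre-specified covariate or stratum, and with a robust (sandwich) variance clustered on patient. Keep the unadjusted model, also with the robust variance, as a sensitivity analysis.

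The text change is about a sentence in each document. The one real cost is data capture. Protocol 6.6 lists medical history only in general terms, and SAP 7.3 refers to whatever the CRF holds, so the documents do not show that the item is recorded for patients who qualify by biomarker. Require yes/no for every patient; this may need one added CRF field and, for patients already enrolled, retrieval from the records. If the item turns out to be uninformative, the loss is about one degree of freedom.

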6.3 Exclusion Criteria

PROTOCOL NUMBER: 2017-05

Patients will be excluded from the study if they meet any of the following:

Exclusion Criteria #	Criteria	Window/Guidanc e
1.	Primarily degenerative MR;	
2.	LVEF ≤ 20% and LVEDD > 80 mm by transthoracic echocardiography as measured by core lab;	Within 30 days of submission to image transfer system and 60 days of procedure
3.	Mitral annular calcification that would impede implantation of device as assessed by core lab;	
4.	Infiltrated cardiomyopathies (e.g., amyloidosis, hemochromatosis, sarcoidosis), hypertrophic cardiomyopathy, constrictive pericarditis, or any other structural heart disease causing heart failure other than dilated cardiomyopathy of either ischemic or non-ischemic etiology;	
5.	Recent hemodynamic instability (e.g. need for inotropic support or intra-aortic balloon pump or other hemodynamic support device);	Within 30 days prior to procedure date
6.	Right sided heart failure or echocardiographic evidence of severe right ventricular dysfunction per core lab assessment;	Per baseline TTE
7.	Estimated pulmonary artery systolic pressure (PASP) > 70 mmHg assessed by site based on echocardiography or right heart catheterization, unless active vasodilator therapy in the catheterization lab is able to reduce the pulmonary vascular resistance (PVR) to < 3 Wood units or between 3 and 4.5 Wood units with V wave less than twice the mean of the pulmonary capillary wedge pressure;	
8.	Other severe valve disorders requiring intervention;	
9.	Need for emergent or urgent surgery for any reason or any planned	From date of

Exclusion Criteria #	Criteria	Window/Guidanc e		
	cardiac surgery within the next 12 months;	signature of informed consent		
10.	Mitral valve anatomy which may preclude proper Edwards Cardioband System access, use and/or deployment;			
11.	Any prior or other planned mitral valve procedure;			
12.	Patient in whom a TEE is contraindicated or screening/baseline TEE is unsuccessful;			
13.	Echocardiographic evidence of intracardiac mass, thrombus or vegetation;			
14.	Severe liver cirrhosis (Childs-Pugh C or MELD > 12);			
15.	Active systemic infection, including active endocarditis;	Within 30 days prior to procedure date		
16.	Untreatable hypersensitivity or contraindication to any of the following:			
	Aspirin and Clopidogrel and Ticlopidine, OR			
	Heparin and Bivalirudin, or Warfarin, OR			
	Nitinol Alloys (nickel and titanium) or contrast media;			
17.	Any recent percutaneous coronary, carotid, endovascular intervention, carotid surgery, or cardiac surgery;	Within 30 days prior to procedure date		
18.	Recent implant or revision of any rhythm management device (i.e., pacemaker, cardiac resynchronization therapy [CRT] with or without cardioverter-defibrillator [CRT-D]);	Within 90 days prior to signing informed consent		
19.	Resting systolic blood pressure < 90 or > 160 mmHg after repeated measurements;	Repeated = 3 consecutive		

Exclusion Criteria #	Criteria	Window/Guidanc e
		measurements
20.	Recent CVA or TIA;	Within 30 days prior to procedure date
21.	Previous stroke with permanent disability (modified Rankin score > 2);	
22.	Severe renal insufficiency with eGFR ≤ 25 mL/min or requiring chronic renal replacement therapy;	
23.	Contraindication to transseptal catheterization;	
24.	Concurrent medical condition with a life expectancy of less than 12 months in the judgment of the investigator;	
25.	Pregnant or planning pregnancy within next 12 months; ¹	
26.	Known bleeding or clotting disorders or patient refuses blood transfusion;	
27.	Severe COPD in whom the primary mechanism of dyspnea is pulmonary disease rather than heart failure;	
28.	Recent myocardial infraction (per WHO definition);	Within 30 days prior to procedure date
29.	Patient has been approved to participate and is currently enrolled in, or has participated in another investigational drug or device clinical study where the primary study endpoint was not reached at time of enrollment;	

 $^{^{}m 1}$ Female patients of childbearing potential need to have a negative pregnancy test performed within 14 days prior to intervention and be adherent to an accepted method of contraception

Exclusion Criteria #	Criteria	Window/Guidanc e
30.	Any condition, in the opinion of the Investigator, making it unlikely the patient will be able to complete all protocol procedures (including compliance with guideline directed medical therapy) and follow-up visits;	
31.	Other medical, social, or psychological conditions that preclude appropriate consent and follow-up, including patients under guardianship.	

6.4 Patient Screening Overview

All patients who have been diagnosed with symptoms of heart failure and mitral regurgitation should be screened for eligibility. Patient will be consented and evaluated against eligibility criteria and baseline testing, as appropriate. Patient eligibility will be reviewed by both the local Heart Team and the study Central Screening Committee (CSC). All potential patients screened for the study will be captured on the site's Screening Log. If a patient does not meet all eligibility criteria, the log shall specify the reason for exclusion. A summary of the screening/enrollment process is provided in Figure 4.

If local IRB approval is obtained, a screening consent form may be implemented to enable the collection of standard assessments for this population (e.g., CT, TEE and TTE.). Data collected from screening assessments may be used to simultaneously assess the patient's anatomic eligibility for this Study using the Cardioband ACTIVE System or other Edwards Clinical Studies using a transcatheter mitral repair or replacement study device. If local IRBs do not allow the use of a screening consent form, all screening assessments will be described under the applicable standard study Informed Consent Form.

6.5 Informed Consent Procedures

Informed consent shall be obtained in writing from the patient or their legally authorized representative and the process shall be documented before any procedure specific to the clinical investigation is applied to the patient. If during the course of the study assessments, a patient is found not to be eligible for inclusion in the study, the patient or their representative should be notified and the reason for ineligibility documented on the screening log/form, and the patient will be exited from the study. Any patient enrolled into the roll-in cohort shall sign the Roll-In ICF which is different from the ICF designated for the randomized study patients.

PROTOCOL NUMBER: 2017-05

The general process for obtaining informed consent (for both screening and study consents, as applicable) is as follows:

- Ensure that the principal investigator or his/her authorized designee conducts the informed consent process;
- Include all aspects of the clinical investigation that are relevant to the patient's decision to participate throughout the clinical investigation;
- Avoid any coercion or undue improper influence on, or inducement of, the patient to participate;
- Not waive or appear to waive the patient's legal rights;
- Use native non-technical language that is understandable to the patient;
- Provide ample time for the patient to read and understand the informed consent form and to consider participation in the clinical investigation;
- Include personally dated signatures of the patient and the principal investigator, or an authorized designee responsible for conducting the informed consent process;
- Provide the patient with a copy of the informed consent form and any other written information; and,
- Ensure important new information is provided to new and existing patients throughout the clinical investigation.

6.6 Screening / Baseline (Pre-Randomization)

Patients who are considered qualified for potential study eligibility will undergo assessments by the local Heart Team as outlined below after signing the appropriate consent form (screening and/or study consent).

- Informed Consent Form (screening and/or study consent)
- Medical History
- NYHA Class
- STS Score
- Cardiovascular Medications assessment
- Modified Rankin score

PROTOCOL NUMBER: 2017-05

- Targeted physical examination
- 12-lead ECG
 - The baseline rhythm will be documented if patients have atrial rhythm (sinus, paroxysmal atrial fibrillation (AF), persistent AF, long-standing AF, and/or permanent AF)
- Transthoracic echocardiogram (TTE); (performed in accordance with core lab imaging acquisition protocol)
- Transesophageal echocardiography (TEE); (performed in accordance with core lab imaging acquisition protocol)
- Cardiac CT Imaging (performed in accordance with core lab imaging acquisition protocol)
- Pregnancy Test (for female patients of child bearing potential)
- Coagulation Panel (PT, PTT; INR for patients on Vitamin-K antagonist)
- Complete Blood Count (WBC with differential, RBC, HCT, Hgb, platelet count)
- Chemistry Panel (BUN, CO₂, Creatinine, Glucose, Cl, K, Na, AST (GOT), ALT (GPT), GGT, serum Total Protein, Albumin, Total Cholesterol, HDL Cholesterol, Uric Acid)
- NT-Pro-BNP or BNP
- Kansas City Cardiomyopathy Questionnaire (KCCQ)
- SF-36v2 Health Survey (SF-36)
- 6 Minute Walk Test (6MWT)
- Adverse Events (adverse events will be collected from the time patient signs informed consent until they complete or exit the study)
- Canadian Study of Health and Aging (CSHA) Clinical Frailty Scale[©]
- Patient Preference Survey
- Activity Monitoring initiation with daily data collection through the 180 day follow-up visit.² Patients may opt out of activity monitoring during the informed consent process or at any time after by notifying the investigator.

² Activity Monitoring components to be implemented at system launch. Patients enrolled prior to system launch will not be required to participate in these assessments.

PROTOCOL NUMBER: 2017-05

Cardiac CT

- Patients will be asked to wear the device as much as possible as waking and sleep activity data will be collected. Daily compliance tracking will be measured as a minimum of 8 hours activity data collection between 6am to 10pm.
- o If the enrolled patient becomes a screen failure at any time after the screening/baseline visit, the patient will be instructed to return the activity monitoring equipment.

Note: The procedures required for Screening/Baseline confirmation may be conducted during more than one visit.

Assessment Window Within 30 days prior to submission to image transfer system TTE and within 60 days prior to procedure* TEE Within 90 days prior to submission to image transfer system

Within 180 days prior to submission to image transfer system

Table 3. Screening/Baseline Assessment Windows

Note: For TTE, TEE and cardiac CT, pre-existing images of adequate quality capturing required anatomy for assessment can be used. If imaging is deemed incomplete or inadequate for assessment, repeat imaging may be required.

